#### 3 Moderate

#### 4. Severe

Table 1 Qualitative and quantitative parameters useful in grading mitral regurgitation severity

	Mild	Moderate	Severe
Structural parameters			
LA size	Normal*	Normal or dilated	Usually dilated**
LV size	Normal*	Normal or dilated	Usually dilated**
Mitral leaflets or	Normal or abnormal	Normal or abnormal	Abnormal/
support apparatus			Flail leaflet/
			Ruptured papillary muscle
Doppler parameters			
Color flow jet area t	Small, central jet	Variable	Large central jet (usually
	(usually $< 4 \text{ cm}^2 \text{ or}$		$> 10 \text{ cm}^2 \text{ or } > 40\% \text{ of I.A}$
	< 20% of LA area)		area) or variable size wall-
			impinging jet swirling in LA
Mitral inflow -PW	A wave dominant*	Variable	E wave dominant b
			(E usually 1.2 m/s)
Jet density - CW	Incomplete or faint	Dense	Dense
Jet contour -CW	Parabolic	Usually parabolic	Early peaking-triangular
Pulmonary vein flow	Systolic dominance §	Systolic blunting 	Systolic flow reversal†
Quantitative parameters*			
VC width (cm)	< 0.3	0.3-0.69	≥ 0.7
R Vol (ml/beat)	< 30	30-44 45-59	≥ 60
RF (%)	< 30	30-39 40-49	≥ 50
EROA (cm  )	< 0.20	0.20-0.29 0.30-0.39	$\geq 0.40$

CW, Continuouswave; LA, left atrium; EROA, effective regurgitant orifice area; LV, left ventricle; PW, pulsed wave; RF, regurgitant fraction; R Vol, regurgitant

#### VI. STUDY PROCEDURES

The surgical procedure may be completed using the valved introducer.

# **Conversion to Standard of Care**

If in the judgment of the operating surgeon, adequate MR reduction has not been achieved, or if for any other clinical reason, conversion to standard of care (SOC) mitral valve surgery via a median sternotomy will be performed. Subjects who undergo a conversion to SOC mitral valve surgery via a median sternotomy will be followed up for 30 days.

**Post-procedure management**: Standard hospital protocols for the management of subjects after mitral valve surgery shall be followed. Unless other indications for anticoagulation are present, all subjects shall receive only aspirin (325 mg/day, beginning on arrival to the intensive care unit).

**Discharge:** All subjects will be discharged from the hospital at the discretion of the attending cardiac surgeon. Prior to dismissal all Subjects will undergo a comprehensive predismissal echocardiogram, as well as a physical assessment (vide supra) in accordance with the schedule of Clinical Investigations.

**Subject follow-up:** Subjects will be seen in the outpatient clinic 30 days (+10 days/-0 days) after the Harpoon procedure. A TTE and a clinical assessment shall be performed at that time (in accordance with the schedule of Clinical Investigations) to evaluate the TSD-5 device against the primary and secondary performance and safety endpoints.

Additional clinical and echocardiographic follow-up in a registry fashion shall occur for all active subjects (in accordance with the Clinical Investigations defined in the table below) at the following intervals:

- 6 months (+/- 30 days),
- 12 months (+/- 30 days)
- 18 months (+/- 30 days)
- 24 months (+/- 30 days)
- 30 months (+/- 30 days)
- 36 months (+/- 30 days)
- 48 months (+/- 30 days) and
- 60 months (+/- 30 days)

If due to an increase of MR, or due to any other medical circumstances, and a study patient has to undergo a Mitral Valve reoperation, this patient will be followed up by the study team for 30 days and then will be exited from the study.

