Currently, mitral valve surgical procedures require a 3 to 6 hour procedure with 4 to 7 days of in hospital recovery (including at least a 1 day in the ICU) and a month or more of recovery before the subject can return to work. With the Harpoon device, the procedure will be transformed in to a 45 to 60 minute procedure where the subject can be discharged within 24 hours and can return to work within a week.

Treatments: At this time, there are treatments available to replace ruptured or elongated cords and result in the reduction of MR; however there is no currently effective medical therapy that treats or cures MR. The current technologies available to address the structural defects of mitral regurgitation include:

- Open heart operations to repair or replace the mitral valve. Open cardiac mitral valve operations require either a sternotomy or a thoracotomy, cardiopulmonary bypass, aortic manipulation and cardioplegic cardiac arrest. Mitral valve repair is carried out with leaflet resectional techniques (Carpentier) or nonresectional techniques using ePTFE cords placed under direct vision. Because the heart is flaccid and arrested, sizing the cords is difficult. Improper sizing of the cords may result in a failed or ineffective mitral valve repair. The success of mitral valve repair is significantly dependent on the expertise of the operating surgeon. For patients with degenerative mitral valve disease, mitral valve replacement is inferior to mitral valve repair (short-term higher perioperative mortality and long term substantially higher risks of stroke and prosthetic valve endocarditis as well as either the need for lifelong anticoagulation (mechanical valve) or the risk of repeat mitral operation (bioprosthetic valve). Mitral valve replacement (compared to repair) is a risk of open cardiac surgery. This procedure is also very invasive and not a feasible option for all patients.
- In 2008, Evalve received CE mark to market the MitraClip in the EU. Shortly thereafter,
  the company was acquired by Abbott Labs. The implantation of MitraClip does not involve
  open-heart surgery, but mimics the surgical method of edge-to-edge valve repair where
  the mitral valve leaflets are clipped together with the device instead of being sutured
  together. Extensive clinical experience with the MitraClip has been collected over the last
  six years and the clinical efficacy has been mixed.

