### V. SUBJECT ENROLLMENT

This is a prospective, nonrandomized, single-centered European study designed single arm study to demonstrate the performance and safety of the Harpoon Medical TSD-5 in Subjects with degenerative mitral regurgitation. A maximum of fifty (50) subjects will be enrolled. The estimated enrollment period is 24 months, and all subjects shall be followed for 30 days, 6 months, 12 months, 18 months, 24 months, 30 months, 36 months, 48 months and 60 months after ePTFE implantation in accordance with the Schedule of Clinical Investigations (see below).

Subject withdrawal from the study: A withdrawal refers to a Subject who is determined to be inactive in the study due to physician discretion, Subject choice (withdrawal of consent), and loss to follow-up or Subject death. Final status will be reported on all Subjects as per the informed consent. Three documented phone calls and a registered/certified letter will be used to assure that there is minimal loss to follow-up. If these efforts to contact the Subject are unsuccessful, the Subject will be considered lost to follow-up.

Pre-procedure/baseline evaluations: All Subjects enrolled in the study will undergo transthoracic echocardiography and transesophageal echocardiography prior to surgery. These are routine preoperative studies for Subjects undergoing heart valve surgery.

Physical Assessment: All study Subjects will undergo a comprehensive history and physical examination. Once enrolled, a physical assessment must be completed within 30 days of the procedure and recorded on a Case Report Form (CRF). In addition to a physical examination and a comprehensive history, the physical assessment will include:

- Vital signs, 12-lead ECG, Laboratory assessment (including WBC count; Hemoglobin; hematocrit; platelet count; creatinine Level, Total Albumin, Total Bilirubin; INR; BNP, NTproBNP) and a chest radiograph (X-Ray)
- A serum pregnancy test for females with childbearing potential (age < 50 years) will be completed within 14 days prior to the procedure.
- As per the standard of care for valve surgery, any subject with symptoms of coronary artery disease and all subjects age >/= 45 years without risk factors shall undergo preoperative diagnostic left heart catheterization ("LHC").
- · Pulmonary Function Tests, when clinically indicated
- 6 Minute Walk test

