#### VII. STATISTICAL ANALYSIS

The sample size for this study was determined using outcomes from available peer-reviewed literature, anticipated improvements in MR reduction at the conclusion of the procedure, at the time of the hospital dismissal and at 30 days and one year. Specifically the percentage of subjects that demonstrate MR reduction from severe to </+ moderate at the conclusion of the procedure and at 30 days. These data will be used to assess the safety and performance of the device when used on a human subject. These data will be used to assess initial safety and performance of the Harpoon Medical TSD-5, and are not designed to test a statistical hypothesis, and therefore a formal sample size has not been calculated. All data will be captured on an intent-to-treat basis. Data will be reported as descriptive statistics.

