# IX. POTENTIAL BENFITS

The Harpoon Medical TSD-5 will provide many significant advantages over current surgical interventions including: 1) a small minimally invasive incision, 2) no sternotomy, 3) no cardiopulmonary bypass, 4) no aortic manipulation, 5) a direct path to the valve plane, 6) performed on a beating heart, 7) real-time TEE-guided chordal length adjustment and 8) less complicated procedure that is teachable and adoptable. The only intracardiac implant is an ePTFE suture which has a 25+ year history of safety in mitral valve repair procedures.

Importantly, the Harpoon approach will not compromise subsequent traditional open-heart mitral valve repair or replacement procedures

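### Safety follow-up stops 30 days after conversion or mitral reoperation, although all subjects are to be followed to 60 months on an intent-to-treat basis

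*Combined protocol and SAP*

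**What the plan says.** Section V (Subject Enrollment) of the combined protocol and SAP, counting from implantation of the cords, states that "all subjects shall be followed for 30 days, 6 months, 12 months, 18 months, 24 months, 30 months, 36 months, 48 months and 60 months". Section VII (Statistical Analysis) adds: "All data will be captured on an intent-to-treat basis".

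Section VI, under Conversion to Standard of Care, sets a different rule for two groups:

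- Converted at the index procedure: "Subjects who undergo a conversion to SOC mitral valve surgery via a median sternotomy will be followed up for 30 days".
- Mitral reoperation later on: "this patient will be followed up by the study team for 30 days and then will be exited from the study".

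The same section says that visits from 6 months onward "shall occur for all active subjects". Section V describes an inactive subject through physician discretion, the subject's choice, loss to follow-up or death. It names neither conversion nor reoperation.

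The secondary safety endpoint in Section III is freedom from SAEs at visits from 6 to 36 months, and Section X has SAEs adjudicated to 36 months. The text on retrospective data collection in Appendix A permits, with consent, data from visits that took place before Versions 03 or 04 were approved. Among exited subjects, it names re-contact only for those who left at 36 months on schedule.

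**The concern.** The two groups whose follow-up is cut short are defined by what happened to the repair. Section VI triggers conversion by inadequate MR reduction or another clinical reason, and reoperation by increased MR or other medical circumstances. The data are therefore missing by design, and for reasons tied to device failure. Each of these subjects has had a transapical procedure performed or attempted, followed by open mitral surgery.

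Section III gives evaluation of safety as the study's purpose. If late SAEs, strokes and deaths are collected only from subjects who needed no open mitral surgery, plus the time before exit for the others, the long-term safety tables will probably look better than the experience of everyone treated. A reader told that the data follow intent to treat would not expect that. The plan also does not say how exited subjects enter the denominators of those tables.

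**Working it through.** **Consistency of the rules.** The plan gives no figure to reproduce: Section VII says that no formal sample size was calculated, and no conversion or reoperation rate is stated. Side by side:

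- Section V: everyone, to 60 months.
- Section VII: intent-to-treat capture, with no duration and no exception.
- Section VI: 30 days after conversion; 30 days and then exit after reoperation (read here as 30 days from the reoperation).
- Section VI limits later visits to active subjects, but Section V's grounds for inactivity do not cover these two events.
- No section sets up SAE or vital-status collection after these exits.

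**Follow-up time lost.** Inputs: N = 50 (the maximum in Section V; the number actually enrolled is not given) and horizons of 36 months (SAE endpoint) and 60 months (last visit). Assumptions: conversion on day 0, reoperation at month 12, and 30 days taken as one month.

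- A conversion loses 36 − 1 = 35 months of 36, or 60 − 1 = 59 months of 60 (98%).
- A reoperation loses 36 − 13 = 23 months, or 60 − 13 = 47 months.
- Planned total: 50 × 36 = 1,800 or 50 × 60 = 3,000 subject-months.

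| Assumed conversions + reoperations | Lost to 36 months | Lost to 60 months |
|---|---|---|
| 2 + 1 | 2×35 + 1×23 = 93 (5.2%) | 2×59 + 1×47 = 165 (5.5%) |
| 4 + 3 | 4×35 + 3×23 = 209 (11.6%) | 4×59 + 3×47 = 377 (12.6%) |
| 6 + 5 | 6×35 + 5×23 = 325 (18.1%) | 6×59 + 5×47 = 589 (19.6%) |

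With fewer than 50 enrolled, the same counts would give larger percentages.

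**Effect on a late-event proportion.** Suppose k of 50 subjects leave at 30 days and a proportion p = 10% of the rest have a late event (both assumed). The retained-only estimate is 10%. For all subjects, the lower bound is p(50 − k)/50 and the upper bound is [p(50 − k) + k]/50.

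- k = 3: 4.7/50 to 7.7/50, or 9.4% to 15.4%.
- k = 5: 4.5/50 to 9.5/50, or 9% to 19%.
- k = 10: 4/50 to 14/50, or 8% to 28%.

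The width is k/50. The bounds are extremes. If exited subjects had two or three times the risk of the others, the value at k = 5 would be (4.5 + 5×0.2)/50 = 11% or (4.5 + 5×0.3)/50 = 12%.

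**The case against.** The best defence is that Section VI is a specific exception to a general schedule, which is ordinary drafting. Section V counts visits from ePTFE implantation, and the intent-to-treat sentence sets no duration. The study is descriptive, and device performance cannot be judged once the valve has been operated on openly. That last point is right for MR grade. It does not explain why SAEs and vital status stop as well, and the text never says that the 60-month commitment excludes these subjects.

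Several parts of the defence do stand, and they limit what a reader may infer:

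- *That the protocol itself names long-term harms for these patients.* Section II mentions "long term substantially higher risks of stroke and prosthetic valve endocarditis", but for valve replacement compared with repair. These risks reach converted or reoperated subjects only if the valve is replaced, and Section VIII describes the fallback as repair. Section II's mortality remark is about the perioperative period, so excess late death is an inference.
- *That late data come only from subjects in whom the device worked.* Subjects with residual or recurrent MR who avoid open surgery stay in follow-up, and reoperated subjects contribute until their exit.
- *That the stated safety endpoint is badly biased.* Under Section I, a conversion or reoperation would probably be an SAE, so the subject has already failed a first-event endpoint. Survival, stroke and total SAEs are not named endpoints, although they are part of any safety evaluation.
- *That nothing later is ever recorded.* Section V promises a final status for all subjects, and Appendix A allows some retrospective collection and provides a separate letter for exited patients. None of this guarantees SAE or vital-status data at the visit dates.
- *That longer follow-up would test the statement that "the Harpoon approach will not compromise subsequent traditional open-heart mitral valve repair or replacement procedures".* A few uncontrolled cases can describe what happened after later open surgery. They cannot prove or refute that claim.

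**Conclusion.** The conflict between Sections V and VII and Section VI is real and should be resolved. Late safety data (mainly total SAEs, strokes and deaths) are not systematically collected after conversion or reoperation. The gap runs from 30 days after the event to the 36-month endpoint horizon; from 36 to 60 months it is a gap in the visit schedule rather than in a stated endpoint. Because exit is linked to device failure, the missing data are likely, but not certain, to favour the device. First-event freedom from SAE is little affected if the conversion or reoperation is itself counted.

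The size is unknown. The range of 5.2% to 18.1% of subject-months to 36 months rests entirely on assumed counts and timing and on 50 subjects. The documents also give no figure for how much higher the risk is in exited subjects.

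**What to change.** 1. Reconcile Sections V, VI and VII: state whom the 60-month commitment covers and how converted and reoperated subjects are counted under intent to treat.
2. Let device echo follow-up end where Section VI says, but keep these subjects in SAE and vital-status follow-up at the existing visit dates. Telephone or record contact is enough.
3. Extend the Appendix A re-consent process to subjects already exited for these reasons, where feasible.
4. Keep all treated subjects in the denominators of the safety tables, count the conversion or reoperation as an event, and show later events separately.
5. Record on the eCRF whether the open operation was a repair or a replacement.
6. Word the statement about later open surgery in Sections II and IX as an expectation.

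The cost is protocol wording, one eCRF field and a few contacts in a single-centre study of at most 50 subjects. The downsides are re-consent of some exited subjects, incomplete recovery of early exits (enrolment closed in November 2017), and possibly less favourable long-term safety figures.

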- In 2013, Neochord released a CE marked, Class III medical device to the EU as a minimally invasive procedure that is performed on a beating heart to replace cords that have become elongated or ruptured. Neochord does not involve open-heart surgery, but mimics the surgical method of suturing the free-edge of the mitral valve to install replacement cords. The surgical entry point is through the apex of the heart for the deployment of a suture by the Neochord device. Initial clinical results have been promising but when the cordal suture is not properly anchored the procedure does not produce a reliable repair.

Version: HMFIM -1000-PL-04, 07 August 2019 Page 5 of 15

Although these procedures are available to a cardiothoracic surgeon in the EU, there is still a need for additional minimally invasive treatment options for patients suffering from mitral valve regurgitation. The MitraClip is limited to an edge-to-edge repair which is rarely used in isolation during open heart operations and has demonstrated mixed clinical efficacy. The large shaft of the NeoChord device creates significant trauma to the left ventricle and the device design limits the placement of the cordal suture to the free edge of the mitral valve leaflet which has impacted the durability of the repair. It is expected that the Harpoon Medical transapical suturing device will be a valuable treatment alternative for patients suffering from mitral valve regurgitation because it can access the left ventricle like the NeoChord device but with a smaller shaft or via a small valved introducer and has a more securing anchoring mechanism that can be deployed anywhere on the mitral valve leaflet.

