# **Performance Goals**:

**Primary Performance Endpoints**: To demonstrate that the TSD-5 performs as designed and has the ability to successfully implant one or more ePTFE cords on the mitral valve via a small left thoracotomy on the beating heart and reduce mitral regurgitation from severe to </= moderate at the conclusion of the procedure and at 30 days post-procedure.

**Secondary Performance Endpoints:** Severity of mitral regurgitation at 6 months, 12 months, 18 months, 24 months, 30 months, and 36 months follow-up shall be tracked and recorded.

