# VIII. RISKS AND DISCOMFORTS

There are risks associated by our protocol. The Harpoon Medical TSD-5 device received CE Mark in December 2017. The study uses minimally invasive surgical techniques to repair/replace cords in a human heart. The discomforts we predict are equivalent to what is expected from similar operative procedures (i.e., localized pain, discomfort at the incision site(s)). Should the Harpoon Mitral Valve Repair System not perform as designed, conventional open-heart procedures will be used to facilitate the repair of the mitral valve.

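### No rule says how MR grades count after a further mitral intervention, and exit depends on an undefined term, so a failed repair can drop out of the late MR summaries unseen

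*Combined protocol and SAP*

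**What the plan says.** Section VI (Conversion to Standard of Care) has two rules for subjects who need other mitral treatment.

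- **At the index procedure:** "Subjects who undergo a conversion to SOC mitral valve surgery via a median sternotomy will be followed up for 30 days".
- **Later, for increased MR or any other medical reason:** if "a study patient has to undergo a Mitral Valve reoperation, this patient will be followed up by the study team for 30 days", the subject then leaves the study. No definition of reoperation is given, and no access route is named.

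Section VIII adds that if the system does not perform as designed, "conventional open-heart procedures will be used to facilitate the repair of the mitral valve".

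On who remains in follow-up, section VI states: "Additional clinical and echocardiographic follow-up in a registry fashion shall occur for all active subjects". The withdrawal paragraph in section V gives four grounds for becoming inactive: a physician's decision, the subject's own choice, lost contact and death. Re-intervention is not among them.

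The late performance endpoint in section III is: "Severity of mitral regurgitation at 6 months, 12 months, 18 months, 24 months, 30 months, and 36 months follow-up shall be tracked and recorded". It sets no threshold for success and has no rule for grades obtained after another mitral treatment. Section VII specifies intention-to-treat data capture and descriptive reporting, and goes no further on this point.

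The background in section II describes other mitral treatments. It says "In 2008, Evalve received CE mark to market the MitraClip in the EU", describes that device as not involving open-heart surgery, and then, after also covering open surgery and NeoChord, remarks: "Although these procedures are available to a cardiothoracic surgeon in the EU".

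**The concern.** Late MR grade is the protocol's only late performance endpoint, and a second mitral treatment acts on it directly. Once a subject has had one, the grade no longer describes the TSD-5 repair alone. The plan needs to say what happens to that subject in the tables, and it does not.

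Two outcomes are possible, depending on how a site reads the word reoperation. If a clip is not regarded as a reoperation, no other rule in the text requires exit. The subject goes on attending echo visits, and the grade after the clip can enter the late table as if the first repair had produced it. If the clip is regarded as a reoperation, the subject leaves after 30 days and is missing from every later visit. Neither outcome shows the failure of the repair in the late MR summary.

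The extension of follow-up adds another way in. Under Retrospective Collection of Data, subjects who completed the 36-month schedule may be contacted again for visits to 60 months, and data from earlier scheduled or unscheduled visits may be gathered. Nothing in that text asks whether the valve was treated again in the meantime.

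**Working it through.** The plan has no figure to reproduce. It states a maximum of 50 subjects, no hypothesis and no formal sample size calculation. The check is therefore a reading of the text, followed by an illustration of size.

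**Reading.** Suppose a subject with recurrent MR receives a clip.

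| Question | Where the answer should be | What is there |
|---|---|---|
| Does the subject exit? | Section VI, follow-up | Depends on an undefined word |
| Does the subject become inactive? | Section V, withdrawal | Not listed; possible at a physician's discretion |
| Does the later MR grade count for the TSD-5? | Sections III and VII | Silent |
| Is the intervention recorded? | Appendix A | No dedicated item; medical history at each follow-up visit |

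**Size.** Let N be the subjects in the late summary, k those with a further mitral intervention and f the other subjects graded worse than moderate. Let s be the number among the k graded moderate or less afterwards. The proportion with moderate or less MR is:

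- (a) kept at the later grade: (N − f − k + s)/N
- (b) exited: (N − f − k)/(N − k)
- (c) counted as failures: (N − f − k)/N

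The differences from (c) are:

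- (a) − (c) = s/N, which lies between 0 and k/N.
- (b) − (c) = k(N − f − k)/[N(N − k)], which also lies between 0 and k/N.

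Neither difference can be negative. At N = 50, the most that one subject can contribute is 1/50 = 2 points.

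In the table N = 50 is the protocol's cap. The values of f and k are assumptions, and s = k (every re-treated subject improves to moderate or less) is the largest case.

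| f | k | (a) kept | (b) exited | (c) failure |
|---|---|---|---|---|
| 0 | 1 | 50/50 = 100% | 49/49 = 100% | 49/50 = 98.0% |
| 0 | 3 | 50/50 = 100% | 47/47 = 100% | 47/50 = 94.0% |
| 0 | 5 | 50/50 = 100% | 45/45 = 100% | 45/50 = 90.0% |
| 5 | 1 | 45/50 = 90.0% | 44/49 = 89.8% | 44/50 = 88.0% |
| 5 | 3 | 45/50 = 90.0% | 42/47 = 89.4% | 42/50 = 84.0% |
| 5 | 5 | 45/50 = 90.0% | 40/45 = 88.9% | 40/50 = 80.0% |

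The last row shows that widening the exit rule would not be enough. Exit removes only 1.1 of the 10 points that separate (a) from (c).

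With fewer subjects in the summary, each one weighs more. At an assumed N = 30 the per-subject limit is 1/30 = 3.3 points. With f = 3 and k = 3 the results are 27/30 = 90.0%, 24/27 = 88.9% and 24/30 = 80.0%.

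**The case against.** The strongest reply is that the text nowhere says a clipped subject remains active or that the clip's result belongs to the TSD-5. A reader might infer that it does, but this is only one reading. The exit rule covers any medical reason and names no access route, so a site could apply it to a clip, or a physician could declare the subject inactive. This part of the reply stands. What remains is that the protocol does not settle the question, and that exit hides the failure as well.

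A reader might also infer that thoracotomy surgery escapes the rules, since section II says "Open cardiac mitral valve operations require either a sternotomy or a thoracotomy" and the conversion rule names only a median sternotomy. The documents do not support this for late operations, because reoperation is not limited by route. At the index procedure, section VIII speaks of conventional open-heart procedures, which under section II include thoracotomy. Only a mismatch between sections VI and VIII is left.

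Nor do the documents make the MitraClip a permitted rescue. Section II is background on available technologies, and the rescue passages that name a treatment name surgery. Nothing in the documents suggests that clip treatment would be common.

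Finally, the event might be visible elsewhere. A hospital admission meets a serious adverse event criterion, freedom from such events is an endpoint to 36 months, and the Clinical Endpoint Committee assesses their relation to the device and procedure. That is true, but it leaves the MR table unchanged, and adjudication stops at 36 months although visits run to 60.

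**Conclusion.** The point holds as a gap in data handling. Exit depends on an undefined term, and no section says how MR after a further mitral intervention enters the late summaries. Compared with counting a failure, both available routes favour the device or make no difference, by at most 2 points per subject at N = 50.

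This size rests on three assumptions: the number of re-treated subjects, for which the documents give no rate; their improvement to moderate or less, where they are kept; and the use of moderate or less as the late summary. The protocol sets that threshold only for the end of the procedure and 30 days. The endpoint affected is secondary and descriptive, in at most 50 subjects. No test is at risk, and no bias has been shown to have occurred. The rule is still worth adding, because the possible error runs in one direction and the remedy is cheap.

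**What to change.** Add a rule for data handling only to section VII, with a cross-reference from the follow-up text in section VI:

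> For any further mitral valve intervention after the TSD-5 procedure, surgical or transcatheter, the date and type are recorded. MR grades obtained afterwards are not attributed to the TSD-5. In the late MR tables the subject stays in the denominator and is shown as a re-intervention (device failure) at that visit and every later one.

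The rule should apply to every late visit that is tabulated, including any data collected retrospectively. It gives the same table entry whether the subject is exited or remains in follow-up, so sites need not agree on what counts as a reoperation.

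The conversion instruction should otherwise stay as it is: enrolment is complete, and the choice of treatment is a clinical matter. Sections VI and VIII describe the operation used at conversion differently, however, and must be reconciled.

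The cost is one case report form item, a short wording change and a possibly slightly less favourable late MR figure. An intervention for a reason unrelated to the repair would also count against the device. Giving re-interventions their own row in the table lets a reader see how many there were.

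### Late MR summaries have no category or rule for subjects exited after mitral reoperation, so tables built from available echoes would leave out reoperated failures

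*Combined protocol and SAP*

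**What the plan says.** Section VI (Subject follow-up) provides that a subject who needs a mitral reoperation, for increased MR or for any other medical reason, leaves the study soon afterwards: "this patient will be followed up by the study team for 30 days and then will be exited from the study". Two neighbouring rules in Section VI also decide who has a late echo:

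- On conversion: "Subjects who undergo a conversion to SOC mitral valve surgery via a median sternotomy will be followed up for 30 days". Conversion may follow inadequate MR reduction, "or if for any other clinical reason, conversion to standard of care (SOC) mitral valve surgery via a median sternotomy will be performed".
- On visits from 6 months: "Additional clinical and echocardiographic follow-up in a registry fashion shall occur for all active subjects".

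The late performance endpoint in Section III is "Severity of mitral regurgitation at 6 months, 12 months, 18 months, 24 months, 30 months, and 36 months follow-up shall be tracked and recorded". Section V grades MR in four classes, from none/trivial to severe. Section VII promises descriptive statistics and says: "All data will be captured on an intent-to-treat basis". It gives no per-visit denominator, no rule for a subject without an echo, and no category for a reoperated or converted subject.

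The withdrawal definition in Section V covers subjects who are "inactive in the study due to physician discretion, Subject choice (withdrawal of consent), and loss to follow-up or Subject death". It does not name conversion or reoperation. The same paragraph does promise that a final status will be reported for every subject.

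**The concern.** Late MR severity is the main performance information from the extended follow-up, and one route out of that follow-up is the outcome itself. A recurrence left alone is graded at the next visit. A recurrence that is reoperated ends the subject's follow-up after 30 days, so it contributes no later grade. For MR-driven exits the distortion favours the device: the grade distribution can look stable because failed repairs were reoperated and left.

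A smaller effect runs the same way. The late visit windows are ±30 days and a reoperated subject stays under study for 30 days. An echo taken in that time could fall in a visit window and be tabulated as a good late result, although it shows the reoperation and not the device. No rule excludes it.

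Conversions at the index procedure bear mainly on the primary endpoint. In the late summaries they only need a labelled category.

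**Working it through.** The plan has no figure to reproduce. Section VII states no hypothesis and no calculated sample size, and no reoperation, conversion or late MR rate appears anywhere. The only count available is the maximum enrolment of 50 (Section V). The rest is assumed, to show how the size behaves.

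**Formula.** Let A be the available echoes at a late visit, p the share of them at moderate or less, and k the subjects exited after an MR-driven reoperation. The moderate-or-less cut-off is borrowed from the 30-day endpoint, because Section III sets none for late visits.

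- Available-echo rate: p
- Rate with the k exits restored as failures: pA/(A + k)
- Overstatement from those exits: p − pA/(A + k) = p·k/(A + k)

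Only when there are no other losses does A + k equal the number attempted, n, so that this becomes p·k/n.

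**No other losses.** Assume n = 50 and 3 severe among subjects still followed.

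| k | Available echoes, ≤ moderate | Exits counted as failures | Gap (points) | Severe, available echoes | Severe or MR-driven reoperation |
|---|---|---|---|---|---|
| 0 | 47/50 = 94.0% | 47/50 = 94.0% | 0 | 3/50 = 6.0% | 3/50 = 6% |
| 1 | 46/49 = 93.9% | 46/50 = 92.0% | 1.9 | 3/49 = 6.1% | 4/50 = 8% |
| 2 | 45/48 = 93.8% | 45/50 = 90.0% | 3.75 | 3/48 = 6.3% | 5/50 = 10% |
| 5 | 42/45 = 93.3% | 42/50 = 84.0% | 9.3 | 3/45 = 6.7% | 8/50 = 16% |

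Check at k = 5: 0.933 × 5/50 = 0.093. The available-echo columns barely move from k = 0 to k = 5, while the share with severe MR or an MR-driven reoperation goes from 6% to 16%.

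**With other losses.** Assume 50 attempted: 35 at moderate or less, 3 severe, 1 converted for inadequate MR reduction, 1 converted for another reason, 4 reoperated for MR, 1 reoperated for another reason, 2 dead, 3 missing.

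- Available echoes: 35/38 = 92.1%
- Four MR-driven reoperations restored: 35/42 = 83.3%
- Gap: 0.921 × 4/42 = 8.8 points. Dividing by 50 instead would give 7.4, which is why A + k is the right denominator.
- Severe MR plus MR-driven reoperation or conversion, of all attempted: (3 + 4 + 1)/50 = 16.0%

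The 35/50 = 70.0% at moderate or less is not the contrast to draw here, because it also counts deaths, missing echoes and events for other reasons against the device.

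**The case against.** Four arguments are fair.

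1. *Intent-to-treat covers it.* The natural reading keeps every enrolled subject in the base. But the sentence concerns how data are captured. It sets no late-visit rule and cannot supply a grade for a subject who has exited.

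2. *Reoperations are reported elsewhere.* This largely stands. A mitral reoperation would ordinarily meet the hospitalization or surgical-intervention criteria for an SAE in Section I. Freedom from SAEs is a named endpoint at 6 to 36 months (Section III). Site-reported events are used where the endpoint committee has not adjudicated (Section X). Final status is promised for all subjects (Section V). None of this feeds the MR table, and both the named SAE endpoint and adjudication stop at 36 months while echoes run to 60.

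3. *Reoperation could be read into physician discretion.* Then the subject is withdrawn, still with no place in the MR summary.

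4. *The study is descriptive and late follow-up is registry-like.* True, and no late success criterion exists. But the tables are then the result, and a reader needs to know who is in them.

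A reader might go further and infer that the plan prescribes available-echo tables, that failures are hidden from the report as a whole, or that the primary result is biased. The documents support none of these. No section prescribes the tabulation, the SAE and status reports would normally show the events, and the primary performance endpoint is read at the end of the procedure and at 30 days, before later reoperations can act on it.

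**Conclusion.** The point holds as a minor one. That the plan is silent on these subjects is clear from the text. It is more than a missing detail, because a stated exit rule makes leaving the MR table depend on the outcome that the table reports.

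The bias itself is conditional. It needs MR-driven exits to occur and late MR to be tabulated from available echoes, and the documents establish neither. Its size from those exits is p·k/(A + k), which is zero with no exits. Under the assumed 50 subjects, 3 severe and no other losses, it is about 1.9 points for one exit and 9.3 points for five. These figures are illustrations, not estimates for this trial.

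**What to change.** Amend Sections III and VII as follows.

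- At each late visit, report all subjects with an attempted procedure in mutually exclusive states: none/trivial, mild, moderate, severe, converted (with reason), mitral-reoperated (with reason), dead, missing.
- Carry conversion and reoperation forward to later visits, so that no data after exit are needed. Do not tabulate an echo taken after reoperation as a device result.
- Beside the active-subjects table, show severe MR plus MR-driven reoperation or conversion as a share of all attempted. Keep events for other reasons, deaths and missing echoes separate.
- Optionally, add the cumulative incidence of mitral reoperation with death as a competing event. If an implanted-only rate is wanted, define implanted first, since a converted subject may already have had cords placed.

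The cost is wording and one table, with no new visits and no change in clinical management. Surgical records and SAE reports supply the events. The downsides are less favourable reported rates and a reason to be classified for each conversion or reoperation.

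Two inconsistencies should be reconciled as separate points. Section V says "all subjects shall be followed for 30 days, 6 months, 12 months, 18 months" and onward to 60 months, while Section VI sets 30-day limits after conversion and reoperation. The late MR endpoint in Section III ends at 36 months, while echoes continue at 48 and 60.
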